## 11.3 Pooling of Sites

As this is a multi-center study, it is possible that some sites may only enroll a small number of subjects. Since this study plans to conduct site-level analyses, the number of subjects at each site may need to be considered for reliable and accurate results. If any site enrolls 5 or fewer subjects, the site will be removed from analyses. Sites enrolling 5 or fewer subjects will still be presented in descriptive statistics analyses.

If no sites enroll 5 or fewer subjects, then the efficacy site-level analyses will be presented for all sites.

Galderma

Protocol number: 43USCH2208

Protocol V4.0

## 11.4 Multiple Comparisons/Multiplicity

No adjustments for multiple comparisons or multiplicity will be made.

## 11.5 Examination of Subgroups

### 11.5.1 Effectiveness

To examine consistency of the results of the analyses of the primary endpoint across different subgroups, the following factors will be used for definition of subgroups, respectively:

- Study site;
- Race (White vs. Black vs. Other); If a subject indicates more than one race, they will be considered 'Other'.
- Ethnicity (Hispanic or Latino vs. Not Hispanic or Latino);
- Sex at Birth (Male vs. Female);
- Age category ( $\leq$  ITT median age vs.  $>$  ITT median age).
- FST (I-III vs. IV-VI); FST Cohort at Randomization will be used to generate FST subgroups.
- Injection volume ( $\leq$  median injection volume vs.  $>$  median injection volume)
- Injection tool (Needle, Cannula, Needle and Cannula)

Subgroup analysis will be performed using the same mixed model as for the primary effectiveness analysis (specified in [Section 9.1.2](#)) but it will also include subgroup factor-by-treatment group interaction term. These analyses will be done using the ITT Population and MI as the imputation method.

Results from the above mixed models will be presented in tables that will display the LS mean estimates with their CIs for each treatment\*factor interaction and the LS mean estimate of the treatment difference within each factor with its standard error and CI.

The number and percentage of subjects in each category of the BE's GCRS, from No Retrusion (0) to Severe Retrusion (3), will also be summarized by visit and subgroup category for each treatment group. The number and percentage of subjects in each change from baseline bin (-3, -2, -1, 0, 1, 2, 3) will be summarized by visit and subgroup category for each treatment group.

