### 3.2.3 Sample Size Justification

Approximately 174 subjects will be treated in the study, randomized in a 2:1 ratio (116 with Restylane Lyft with Lidocaine: 58 with Juvéderm Voluma XC).

For sample size calculation of 174, it was assumed that the true effectiveness of Restylane Lyft with Lidocaine compared to control treatment assessed by the GCRS is approximately 0.1 point lower. A common standard deviation of 0.7 point was assumed for the treatments. Based on the non-inferiority margin of 0.5, a total sample size of 147 evaluable subjects is then required to show non-inferiority of Restylane Lyft with Lidocaine to the control treatment with a power of 90%, using a two-sided 95% CI for the difference between treatment means.

The GCRS scale is designed so that a complete scale step considers a meaningful clinical difference. A change of up to 0.5 points is not considered clinically important, thus, the non-inferiority margin of 0.5 is chosen. We have estimated the standard deviation from previous studies where the scale GCRS has been used.

Accounting for approximately 15% dropouts and non-evaluable subjects due to protocol deviations at 3 months, a total of approximately 174 subjects will be randomized in the study.

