## 11.6 Multiple Imputation Method

The MI procedure will be performed for the primary analysis using the following methods:

Missing data for 3 months after last treatment Blinded Evaluator GCRS assessment will be imputed using MI under the Missing at Random (MAR) assumption. Change from Baseline in Blinded Evaluator 3 months after last treatment GCRS will be derived from the corresponding imputed values. The following steps will be followed to create the imputations:

1. Regardless of the actual pattern of missing data, the Markov Chain Monte Carlo (MCMC) method of the SAS PROC MI procedure will first be used to make it monotone. The single chain method will be used. The minimum values for imputed variables will be set to 0, in order to force PROC MI to redraw another value for imputation when an intended imputed value is less than the 0, the maximum value for imputed variables will be set to 3, in order to force PROC MI to redraw another value for imputation when an intended imputed value is greater than the 3. Imputed values will be rounded to the nearest integer. The seed number will be set to 2208 and 5 imputations will be created.
2. The SAS PROC MI will be used for imputing missing values of data with monotone missing pattern. One imputation will be made using each of the 5 MCMC-imputed datasets (Step 1). A linear regression model will be used with covariates for treatment, site, race group, ethnicity, sex, Fitzpatrick Skin Type, age, total injection volume, and non-missing GCRS values from earlier scheduled time points including Baseline. The minimum values for imputed variables will be set to 0, in order to force PROC MI to redraw another value for imputation when an intended imputed value is less than the 0. Imputed values will be rounded to the nearest integer. The seed number will be set to

Galderma

Protocol number: 43USCH2208

Protocol V4.0

2208. Change from Baseline in 3 months after baseline GCRS will be derived from the corresponding imputed values. The Lost to Follow Up subjects who were reenrolled described in [Section 9.1.1](#) and [9.1.2](#) will be handled assuming No Change from Baseline after the missing values have been imputed with multiple imputation. Protocol deviations will be used to identify subjects who missed their primary endpoint visit due to being Lost to Follow Up and later reenrolled.

3. The imputed datasets will be analyzed as specified in [Section 9.1.2](#).

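### The subgroup interaction models run on data imputed without treatment-by-factor terms or injection tool, which modestly pulls subgroup differences toward the overall result

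*SAP*

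**What the plan says.** SAP 11.5.1 lists eight subgroup factors for the primary endpoint: site, race, ethnicity, sex at birth, age, Fitzpatrick skin type (FST), injection volume and injection tool. The model is the primary one, except that "it will also include subgroup factor-by-treatment group interaction term". On the data to be used it says "These analyses will be done using the ITT Population and MI as the imputation method". The output is LS means, treatment differences within each level, standard errors and confidence intervals. Counts of each change-from-baseline value by visit, subgroup and arm are also tabulated.

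The only imputation specification is SAP 11.6, written for the primary analysis. An MCMC step first makes the missing pattern monotone. Then "A linear regression model will be used with covariates for treatment, site, race group, ethnicity, sex, Fitzpatrick Skin Type, age, total injection volume", together with earlier GCRS values including Baseline. No interaction is named and injection tool is not listed. No separate imputation is described for the subgroup models. The observed-case, BOCF and worst-case analyses in SAP 9.1.3 and 11.1 are for the overall primary analysis.

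**The concern.** The analysis model contains a term that the imputation model leaves out. If the treatment difference really varies by a factor, a score drawn from a regression without that interaction reflects the average difference, not the one in that subject's subgroup. Adding such scores moves each subgroup's estimate toward the overall one, which is toward the consistency being examined.

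Earlier scores do not repair this in the regression step. SAP 3.2.4.1 schedules the Blinded Evaluator's GCRS at Screening, Baseline and then Month 3, so no Blinded Evaluator score between treatment and Month 3 carries information about response.

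At stake is how well the subgroup display can show a deficit in a small group such as FST IV-VI, where the planned minimum is 35 of 174 subjects.

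**Working it through.** **The plan's own figure.** The SAP gives no figure for the subgroup analysis, so I checked the sample size that supplies the missing-data allowance. SAP 3.2.3 states "Based on the non-inferiority margin of 0.5, a total sample size of 147 evaluable subjects is then required", "A common standard deviation of 0.7 point was assumed for the treatments", a true effectiveness that "is approximately 0.1 point lower", and testing "with a power of 90%, using a two-sided 95% CI for the difference between treatment means", with 2:1 allocation.

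- Control arm: (1 + 1/2) × 0.7² × (1.960 + 1.282)² / (0.5 − 0.1)² = 48.3, rounded up to 49. Total 3 × 49 = 147, which reproduces.
- Allowance: "Accounting for approximately 15% dropouts and non-evaluable subjects due to protocol deviations at 3 months". 147 / 0.85 = 173, against 174 stated (116:58). The implied loss is 1 − 147/174 = 15.5%.

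That 15% includes protocol-deviation exclusions, so the planned share of missing Month 3 scores is no higher than 15%.

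**Formula.** With missing share m in a subgroup and imputed scores carrying the overall difference D, the expected subgroup difference is (1 − m) × true + m × D. With equal m in both levels, D cancels and the expected interaction is (1 − m) × true.

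**Assumptions not in the documents.** True interaction 0.50 grade; missing shares as shown; residual SD 0.65 or 0.68; a two-level factor split 20/80 (35/174 = 20%) or 50/50; five imputations, as in SAP 11.6; missingness unrelated to outcome given the factor. Each simulated trial has 174 subjects, 2:1. The simulations cover the regression step only.

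| Missing | (1 − m) × 0.50 | Simulated, 20/80 | Simulated, 50/50 | Observed cases |
|---|---|---|---|---|
| 5% | 0.475 | 0.48 | 0.475 | about 0.50 |
| 10% | 0.450 | 0.44 to 0.46 | 0.451 | about 0.50 |
| 15% (15.5% in 50/50) | 0.425 (0.423) | 0.42 to 0.43 | 0.420 | about 0.50 |

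Further results:

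- Adding the treatment-by-factor term to the imputation restores 0.50 (0.502, 0.502 and 0.499 in the 50/50 runs).
- With the factor absent from the imputation altogether, as for injection tool, and 15.5% missing: 0.417, against 0.497 once the factor and its interaction are added.
- With scores rounded to whole grades and held to 0-3, at 15.5% missing: 0.334, against 0.399 for observed cases. That is 1 − 0.334/0.399 = 16% shrinkage, the same proportion.
- Unequal loss, 30% in a 20% subgroup and 12% elsewhere: observed weights are 0.14 and 0.704, or 0.166 and 0.834. The expected interaction is (0.70 × 0.834 + 0.88 × 0.166) × 0.50 = 0.365. Simulation gave 0.370, against 0.515 with the term added.

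**Against the noise (20/80).** The standard error of the interaction is 0.27 to 0.29. The bias of about 0.03, 0.05 and 0.07 at 5%, 10% and 15% is therefore 0.1 to 0.25 of a standard error. Interval coverage under the SAP imputation stayed at 95.5% to 96.3%. If a 5% interaction test were run at 15% missing, its power would be 0.30, against 0.40 to 0.44 with observed cases or the term added.

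**The case against.** The strongest reply is that this hardly matters. The bias is small against the standard error and coverage holds. Root mean square error is slightly lower under the SAP imputation than with the interaction added (0.265 against 0.273 at 5% missing, 0.266 against 0.284 at 15%). The change-from-baseline counts by subgroup and arm, if read as observed data, let a reader work out mean changes directly. All of this stands, and it limits the point to a cheap improvement. It does not remove it: the tables with modelled differences and intervals are the ones that carry the shrinkage, and no observed-case version of them is planned.

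Several stronger readings are tempting, and the documents do not support them.

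- A reader might infer that every missing subject receives the common effect. SAP 11.6 does not list the variables in the MCMC step. If later visits are included, a subject who misses Month 3 but returns later may have Month 3 filled partly from their own later scores. Re-enrolled lost-to-follow-up subjects are set to no change (SAP 9.1.1 and 11.6). Imputing separately by arm would supply interactions for the listed factors, though not for tool, but it is not stated.
- A reader might infer that the bias always favours consistency. The calculations show this only under the missingness assumed above.
- A reader might infer that consistency is formally tested. SAP 11.5.1 states no interaction p-value, threshold or decision rule.
- A reader might take needle-and-cannula users for a small subgroup. The documents give no distribution of injection tool.

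**Conclusion.** The point holds in limited form. Month 3 scores drawn from the SAP 11.6 regression carry a common treatment effect, so the modelled subgroup differences in SAP 11.5.1 shrink by roughly the fraction imputed: about 5%, 10% and 15% of the true interaction at those missing shares. The 15% case is an upper planning figure. Shrinkage would be larger if losses concentrate in one small subgroup. The sizes rest on an assumed 0.50 interaction and on missingness at random given the model covariates. It would be wrong to read this as a threat to the main conclusion: non-inferiority rests on the overall ITT and PP comparisons (SAP 9.1.2), which have no subgroup term.

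**What to change.** In SAP 11.5.1, state that the same interaction models will be fitted on observed cases in the ITT Population, either as the main subgroup analysis or reported beside the imputed version. This removes the shrinkage when data are missing at random given the covariates in the subgroup model.

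If multiple imputation stays as the main version, add injection tool and, where cells allow, the treatment-by-factor term to the imputation used for that factor. Cells may be too thin for this by site and by race. They may also be thin for tool, since the SAP lists a cannula-only level while Section 3.2 requires a needle in the pogonion. That makes the observed-case version the simpler choice. Leave the primary imputation unchanged.

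The cost is one extra set of subgroup tables and slightly more variable subgroup estimates. No new data are needed.

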### 11.5.2 Safety

The consistency of AE data across different subgroups will be evaluated. The following subgroup factors will be used:

- Study site;

Galderma

Protocol number: 43USCH2208

Protocol V4.0

- Race (White vs. Black vs. Other); If a subject indicates more than race, they will be considered 'Other'.
- Ethnicity (Hispanic or Latino vs. Not Hispanic or Latino);
- Sex at Birth (Male vs. Female);
- Age category ( $\leq$  Safety Population median age vs.  $>$  Safety Population median age).
- FST (I-III vs. IV-VI); FST Cohort at Randomization will be used to generate FST subgroups.
- Injection volume ( $\leq$  median injection volume vs.  $>$  median injection volume)
- Injection tool (Needle, Cannula, Needle and Cannula)

For the injection volume subgroup analysis, the median injection volume will be computed for the Injection Timepoint defined in [Section 4.5.2](#).

Related AEs will be summarized within each subgroup by SOC, PT and maximum intensity.

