9.6.2 Safety

CONFIDENTIAL

Page 69 of 88

Effective

Version: 4.0

Effective date: 2023-05-24 22:48

The consistency of AE data across different subgroups will be evaluated. The following subgroup factors will be used:

- Study center
- Race
- Ethnicity
- Sex at birth
- Age (\leq median age vs $>$ median age)
- FST I-III and IV-VI
- Injection volume (\leq median total injection volume vs $>$ median total injection volume)

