### 3.2 Overall Design

This is a prospective, randomized, evaluator-blinded, parallel group, comparator-controlled, multicenter study in the US to evaluate the safety and effectiveness of Restylane Lyft with Lidocaine for augmentation of the chin region to improve the chin profile. The chin region is comprised of the anatomical areas of the pogonion, menton, and pre-jowl sulcus. Before the study starts, a randomization list will be prepared under the supervision of a designated biostatistician from the Sponsor.

Injection technique is at the Treating Investigator's discretion with needle only or a combination of needle and cannula. Restylane Lyft with Lidocaine and the comparator-

Version: 1.0

Effective

Galderma

Protocol number: 43USCH2208

Protocol V4.0

control will be administered by needle in the pogonion. The mentum and pre-jowl sulci may be injected by needle or cannula.

At least 35 subjects will be Fitzpatrick skin type (FST) IV through VI, this includes at least 18 subjects with FST V – VI, where at least 9 subjects will be FST V and at least 9 subjects will be FST VI.

After providing informed consent, eligible subjects randomized to receive either Restylane Lyft with Lidocaine or a comparator-control will be injected by the Treating Investigator at Baseline (Day 1). A follow-up telephone call should be made 72 hours after treatment and a follow-up visit should be scheduled after 14 days.

Optional touch-up treatment may be administered 1 month (4 weeks) after initial treatment, if deemed necessary by the Treating Investigator and the subject to obtain optimal aesthetic improvement. If optional touch-up is performed, a 72-hour follow-up telephone call, a follow-up visit at 14 days, and a follow-up visit at 1 month should be scheduled.

Appropriate injection volume for the chin area will be determined by the Treating Investigator but is not to exceed a maximum total volume of 4.0 mL for initial and touch-up treatments combined. Injection in the pogonion is only permitted with a needle. Both needle and cannula are permitted for injection in the other treatment areas.

Investigator blinding will be accomplished by using a Treating Investigator to administer the treatments and a Blinded Evaluator, to whom randomization and treatment are concealed, to conduct the blinded assessments. Safety assessments will be performed by non-blinded personnel.

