### 3.2.1 Randomization Methodology

Approximately 174 subjects will be randomized (2:1) to treatment with either Restylane Lyft with Lidocaine (Treatment Group) or Juvéderm® Voluma™ XC (Control Group).

Before starting the study, a computer-generated randomization list will be prepared under the supervision of a designated biostatistician from the Sponsor. The randomization will be stratified by FST (I-III, IV or V-VI). Subjects in the FST I-III stratum will be further stratified by study site; subjects in the FST IV, or FST V-VI strata will not be further stratified by study site due to the smaller sample size in these groups.

Randomization will be performed using an Interactive Response System by assigning each subject to treatment with Restylane Lyft with Lidocaine or Juvéderm Voluma XC

Galderma

Protocol number: 43USCH2208

Protocol V4.0

according to the randomization list. Randomization numbers will be allocated in ascending sequential order to each subject.

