## 8 Demographic and Baseline Characteristics

### 8.1 Demographic Characteristics

Demographic assessments for this study include:

- Age (years);
- Age Category ( $\leq$  ITT Population median age,  $>$  ITT Population median age);
- Sex at Birth (Male, Female);
- Gender identity (Female, Male, Transgender male-to-female, Transgender female-to-male, Gender nonconforming (neither exclusively male nor female), Other, Decline to answer);
- Ethnicity (Hispanic or Latino, Not Hispanic or Latino);
- Race (White, Black or African American, Asian (Chinese, Asian Indian, Filipino, Japanese, Korean, Vietnamese, Other Asian), American Indian or Alaska Native, Native Hawaiian or Other Pacific Islander, Other);
- Height (cm);
- Weight (kg);
- BMI ( $\text{kg}/\text{m}^2$ );
- Fitzpatrick Skin Type (FST) Score (I, II, III, IV, V, VI);
- Fitzpatrick Skin Type (FST) Cohort at Randomization (I-III, IV, V-VI);
- Baseline GCRS by Blinded Evaluator (0, 1, 2, 3);
- Baseline GCRS by Treating Investigator (0, 1, 2, 3).

Demographic and Baseline characteristics will be summarized using the ITT Population. No formal statistical comparisons between treatment groups will be performed. Continuous variables to be summarized include age (in years), height (in cm), weight (in kg), BMI (in  $\text{kg}/\text{m}^2$ ). Categorical variables include age category, gender, ethnicity, FST, Baseline GCRS by Blinded Evaluator and Baseline GCRS by Treating Investigator.

FST Cohort at Randomization will be used in tables. FST Cohort at Randomization and FST Score will both be included in listings.

Demographic and Baseline characteristics, as well as the childbearing potential and breastfeeding status for female subjects will also be reported in a data listing.

Galderma

Protocol number: 43USCH2208

Protocol V4.0

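### The FST subgroup outputs collapse the three randomisation strata to I-III vs IV-VI, take skin type from the randomisation entry, and summarise only related AEs

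*SAP*

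**What the plan says.** - **Strata.** SAP 3.2.1 and Protocol 5.5 use three FST strata: "The randomization will be stratified by FST (I-III, IV or V-VI"). Only the I-III stratum is further stratified by site.
- **Minima.** SAP 3.2 and Protocol 3.1 set enrolment floors: "At least 35 subjects will be Fitzpatrick skin type (FST) IV through VI", of whom at least 18 are V-VI, and "at least 9 subjects will be FST V and at least 9 subjects will be FST VI".
- **Subgroups.** SAP 11.5.1 (effectiveness) and 11.5.2 (safety) use the same rule: "FST (I-III vs. IV-VI); FST Cohort at Randomization will be used to generate FST subgroups". The protocol synopsis and Protocol 9.6.1 and 9.6.2 (so numbered under section 9.7) had already specified the two levels I-III and IV-VI. The SAP adds the source variable.
- **Baseline tables.** SAP 8.1 lists both the six-level FST Score and the three-level cohort as demographic items, then states "FST Cohort at Randomization will be used in tables". Both variables go into listings.
- **AE output by subgroup.** Protocol 9.6.2 says "The consistency of AE data across different subgroups will be evaluated", and SAP 11.5.2 repeats the commitment. The output that SAP 11.5.2 then describes is narrower: "Related AEs will be summarized within each subgroup by SOC, PT and maximum intensity". SAP 15.2, which records changes from the protocol, does not mention this narrowing.

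**The concern.** The trial controls enrolment and allocation at a finer skin-type level than it reports. Three things follow.

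1. A pattern specific to types V-VI is averaged with type IV in every planned FST subgroup table. No minimum or cap is set for type IV alone, so the degree of averaging depends on recruitment.
2. The subgroup label comes from what was entered at randomisation. If that entry differs from the recorded FST Score across the III/IV boundary, the subject's AEs are counted under the wrong skin type. Neither a rule for mismatches nor a check by recorded score is described.
3. An AE judged unrelated appears in no subgroup summary. Relatedness is the Investigator's judgement, and Protocol 5.6 leaves the Treating Investigator unblinded. AESIs are defined regardless of relationship (SAP 10.2.5), yet one judged unrelated would drop out of the subgroup tables. This affects all eight subgroup factors in SAP 11.5.2, not only FST.

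At stake is how clearly the report can describe safety by skin type. The primary comparison is not at issue.

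**Working it through.** **The plan's own sample size first.** Inputs from SAP 3.2.3: margin 0.5, SD 0.7, true difference 0.1 against Restylane Lyft, two-sided 95% CI, 90% power, allocation 2:1, 15% loss.

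- Control n = (1.960 + 1.282)² × 0.7² × (1 + 1/2) / (0.5 − 0.1)² = 48.3, rounded up to 49. The total is 3 × 49 = 147, as stated.
- 147 / 0.85 = 172.9, so 173, which becomes 174 for a 2:1 split. The stated figures reproduce.

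**Subgroup sizes at the minima, split about 2:1.** IV-VI: 35, about 23 vs 12. V-VI: 18, about 12 vs 6. Type IV: 35 − 18 = 17, about 11 vs 6.

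**Dilution.**

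- V-VI share of the pooled group = 18/35 = 51%, so a V-VI departure from type IV of size d appears as about 0.51d.
- If 35 type IV subjects enrolled (an assumption), the share would be 18/53 = 34%.
- The table shows pooled AE rates. The AE rates are assumed, because the documents give none by skin type.

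| Rate in V-VI | Rate in IV | Share of V-VI | Pooled rate |
|---|---|---|---|
| 20% | 5% | 51% | 12.7% |
| 30% | 10% | 51% | 20.3% |
| 20% | 5% | 34% | 10.1% |

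**What a zero count would mean.** The two-sided 95% upper limit with no events in n subjects is 1 − 0.025^(1/n). For 23 pooled Restylane subjects it is 14.8%, and for the 12 of type V-VI it is 26.5%. This is purely an effect of sample size. It shows that a pooled zero must not be read as if it applied to V-VI.

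**What a V-VI row could support.**

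- AEs: the chance of at least one event among 12 subjects is 1 − (1 − p)^12, which is 72% at a true rate of 10% and 46% at 5%.
- GCRS change: SE = 0.7 × √(1/12 + 1/6) = 0.35. The 95% half-width is 0.69 (normal) to 0.74 (t), against a margin of 0.5, and power for non-inferiority is about 19%. For pooled IV-VI at 23 vs 12, the half-width is 0.49 to 0.51 and power about 34%.

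**Which entry errors matter.** Under the planned two-level split, confusing IV with V leaves a subject in IV-VI. Only a III/IV error moves a subject, and each one is 1/35, or about 3%, of a 35-subject group. In separate IV and V-VI rows, IV/V errors would matter too, so the recorded score becomes more important once those rows exist.

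**Which minima can be checked from tables.** A three-level cohort table shows the 18 and the 35 as entered at randomisation. The cohort has no level separating V from VI, so the 9 and 9 can be confirmed only from the listed FST Score.

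**The case against.** The strongest reply is that the SAP does what the protocol prespecified. The I-III vs IV-VI split is in the protocol for both effectiveness and AEs, stratification secures balance without promising a subgroup analysis, and the minima are enrolment quotas. That stands: there is no contradiction on the grouping.

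Four stronger readings are tempting, and the documents do not support them.

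- *A reader might infer that V-VI results cannot be read at all.* They can be rebuilt. FST Score and cohort are both listed (SAP 8.1), all AEs are listed with intensity and relatedness (SAP 10.2), and GCRS ratings are listed by subject (SAP 9.2.1).
- *A reader might infer that the quotas exist to support a conclusion about V-VI.* No such objective or hypothesis is stated.
- *A reader might infer that the SAP keeps two FST variables because mismatches are expected.* SAP 8.1 gives no reason, and no mis-stratification is documented.
- *A reader might infer that pooling is what prevents a V-VI effectiveness conclusion.* At 12 vs 6 the sample size prevents it, pooled or not.

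On AEs, it is fair to add that all AEs are tabulated by SOC and PT in the whole Safety Population (SAP 10.2.1), that missing relatedness counts as related (SAP 10.2.3), and that the Sponsor also assesses causality (Protocol 7.9.5). Unblinding concerns treatment arm and does not by itself hide a skin-type pattern. What remains is that the commitment covers AE data while the described subgroup output covers related AEs only.

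Table shells are in a separate document, and Protocol 9.5 cannot be read in the released text. The statements here about tables therefore concern what the protocol and SAP describe.

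**Conclusion.** The concern holds as a reporting gap, mainly for safety. The described subgroup tables have no row for V-VI, although V-VI is a randomisation stratum with its own minimum. At the minima about half of a V-VI departure from type IV would be visible in the pooled row, and about a third if 35 type IV subjects enrolled (assumed). V-VI results by subgroup, and the 9 and 9 minima, are recoverable only from listings. Restricting the subgroup summary to related AEs is narrower than the commitment in Protocol 9.6.2 and is not recorded as a change.

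The sizes assume enrolment at the stated minima and a 2:1 split within strata, and the AE rates are illustrative. The point about the randomisation entry is conditional: it matters only if entry and recorded score disagree across III/IV. The primary analysis and its type I error are unaffected.

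**What to change.** 1. **SAP 11.5.1:** keep I-III vs IV-VI for the treatment-by-subgroup model. Optionally add descriptive GCRS change for IV and V-VI, with no test.
2. **SAP 11.5.2:** add descriptive rows for IV and V-VI, with no test, and keep IV-VI as a combined row.
3. **Source variable:** build FST subgroups from the recorded FST Score, and keep the cohort as the stratification factor. State how many subjects have a score that disagrees with their cohort.
4. **SAP 8.1:** tabulate FST I to VI as well as the cohort, so that the V and VI minima are visible.
5. **SAP 11.5.2:** summarise all AEs as well as related AEs for each subgroup factor.

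No new data are needed: the score is already collected and the cohort already has three levels. The cost is one further AE table per subgroup factor, a few extra rows, and subgroup counts that may differ from stratum counts if entries disagree. The V-VI cells will be small (about 12 vs 6), with a GCRS half-width of about 0.7 against a margin of 0.5, so the table should be labelled descriptive.
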